- The informed consent process will be conducted by trained research staff and will include all aspects of the study and a full disclosure of the risks, benefits, procedures, and alternatives. The study consent and HIPAA authorization will be signed after all questions have been discussed and answered. Collection of baseline information, including such items as contact information, BP measurements, demographic and pregnancy history information, concomitant medications, and lifestyle information will follow the informed consent process.
- All data will be kept confidential to comply with HIPAA regulations. No
 patient identifiers will be included in the data sets. All data will be kept in a
 password protected folder within the ARMC network and will only be made

- available to study investigators. The database will be controlled, and password-protected.
- All data and records will be kept confidential in accordance with Institutional policies and HIPAA. There will be extremely limited access to subject information. All data will be anonymized before publication. Patient Data Sets will include identifiers that are strictly limited to medical record number, ethnicity, age and sex, along with associated clinical data. Patient Data Sets will be imported into password protected Excel files located in an encrypted folder accessible only to the investigators involved in the study, IRB, and IT on the ARMC server. All published poster presentations, abstracts and papers will be de-identified, with a medical record numbers and any other identifying material removed. Patient's age, parity, sex and race will be used in publication for educational purposes.

VI: Study Design and analysis:

- All patients admitted for term induction of labor will be asked to participate if they
 meet the inclusion criteria as described above. Once consented, the participants
 will be randomly allocated into two groups: control versus intervention group.
 Randomization will be done as block randomization based on maternal BMI at
 time of admission, all odd patients will be enrolled into the control group and all
 even study numbers will be in the intervention group.
 - -Control group: no medication

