 - -Intervention group: Calcium carbonate 500 mg 4 tablets PO x1 -Calcium carbonate (TUMS) is an over-the-counter antacid medication and common side effects include changes in bowel habits like constipation or diarrhea, bloating, gas, and abdominal discomfort. Rare side effects include allergic reactions and hypercalcemia if taken in large amounts. The daily recommended max dose is 8000mg, we will be giving a max of 2000 mg.⁷
- The primary outcome will determine the effect of calcium carbonate on uterine contraction strength, assessed by comparing Montevideo units (MVU), frequency of contractions, and peak of the contractions 30 minutes before medication administration and at 30 minutes interval for a total of 2 hours afterward. To ensure accuracy in MVU measurement, all patients should already have an intrauterine pressure catheter (IUPC) in place at the discretion of the OB provider before they are enrolled. Secondary outcomes include duration of first and second stage of labor, mode of delivery, neonatal outcomes (NICU admission, low APGAR scores), and maternal outcomes (PPH).
- Other maternal information such as height, weight, BMI, age, parity, race, gestational age, cervical dilation/effacement/station at the time of medication administration and after administration, time to delivery, oxytocin use, epidural use, Apgars, perineal laceration, QBL, birthweight, mode of delivery, delivery complications will be obtained to compare among the two groups to make sure there are no confounding factors. Since Pitocin dose is a confounding variable after receiving the medication, patients must be off Pitocin during study period.

- The data collected will be divided into 2 groups: control versus intervention group. Statistical analysis included descriptive statistics to summarize maternal characteristics and clinical outcomes. Normality testing was performed, and appropriate comparative statistical tests were selected, including two-way Student's t-tests, Tukey's tests, or post hoc Student–Newman–Keuls tests as appropriate. A p-value of less than 0.05 was considered statistically significant. Univariate and multivariate linear regression analyses were conducted to identify associations between maternal, fetal, and labor-related variables and study outcomes.
- Uni- and multivariate analysis with linear regression modeling will be used to identify significant associations between maternal, fetal, or labor characteristics.

VII: Risks and Benefits:

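### The primary readings are timed from a dose that controls do not receive, so the control arm has no time zero, and the plan does not say how baseline or the repeated readings enter the comparison between arms

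*Combined protocol and SAP*

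**What the plan says.** All of the following is in section VI, Study Design and analysis, unless stated otherwise.

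- **Timing.** The primary outcome compares MVU, contraction frequency and contraction peak "30 minutes before medication administration and at 30 minutes interval for a total of 2 hours afterward". The cervical findings are collected on the same clock: "cervical dilation/effacement/station at the time of medication administration and after administration".
- **Control arm.** "Control group: no medication". No placebo, sham, nominal dosing time, allocation-based clock or blinding is described.
- **Oxytocin condition.** "Since Pitocin dose is a confounding variable after receiving the medication, patients must be off Pitocin during study period". The start of that study period is not given.
- **Catheter.** "all patients should already have an intrauterine pressure catheter (IUPC) in place at the discretion of the OB provider before they are enrolled".
- **Tests.** "appropriate comparative statistical tests were selected, including two-way Student's t-tests, Tukey's tests, or post hoc Student–Newman–Keuls tests as appropriate".
- **Regression.** "Univariate and multivariate linear regression analyses were conducted to identify associations between maternal, fetal, and labor-related variables and study outcomes". Neither study arm nor baseline MVU is named as a term.
- **Allocation.** The text begins "Randomization will be done as block randomization based on maternal BMI at" the time of admission, then assigns odd study numbers to control and even numbers to intervention.

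Section V (subject recruitment) sizes the trial at 40 per group, for a 20% difference on a baseline of 200 MVU with 80% power. It gives no SD. It does not say whether the 40 MVU refers to one reading, a mean or a change.

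**The concern.** The trial asks whether contractility differs between arms after a common starting point. As written, that point exists in one arm only, so the primary outcome cannot be measured in half the sample by the stated rule. Someone must supply a control clock, such as consent, allocation, or a time picked later from the trace. These events can be separated in time, and nothing makes the gap equal to the delay before ingestion in the other arm. If contractility changes as labor advances, a systematic difference in where the clock starts enters the treatment contrast even though the women were randomized.

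The second gap concerns the test. The outcome definition sets the pre-dose reading beside the later ones, so baseline is part of the intended comparison. Its statistical form is open: change score, covariate, or a before-after test within each arm. No primary time point and no summary over the two hours is named, so the error rate and the precision depend on a choice made later.

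**Working it through.** **Inputs from the documents.** 40 per arm; planned difference 0.20 × 200 = 40 MVU; power 80%; significance level 0.05, taken as two-sided. **Assumptions.** Drift of 10-30 MVU per hour; systematic mismatch of 30 or 10 minutes; correlation between readings of 0.3, 0.5 or 0.7, either equal or decaying with time (AR(1)); four follow-up readings, at 30, 60, 90 and 120 minutes. The documents give none of these values, and four readings is an interpretation of the schedule.

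**1. The plan's own figure.** N = 80 cannot be reproduced forward, because no SD is stated. Working back, 40 per arm gives 80% power by t-test at a standardized difference of 0.634, so SD = 40/0.634 = 63 MVU.

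**2. Shift from a mismatched clock.** Shift = drift × mismatch.
- 30 minutes: 10 × 0.5 = 5 to 30 × 0.5 = 15 MVU, which is 13-38% of 40.
- 10 minutes: 10/6 = 1.7 to 30/6 = 5 MVU.

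These are shifts in the unadjusted difference. If the baseline moves with time zero, a change score under linear drift cancels the shift completely (0 MVU). ANCOVA removes a share equal to its slope on baseline: 0.30/0.50/0.70 (equal correlation) or 0.11/0.23/0.44 (AR(1)). If the baseline does not move with time zero, neither method removes any of it.

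**3. False-positive rate under a shift.** Noncentral t with 78 df and noncentrality = shift / (SD of the analysed quantity × √(2/40)).

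| SD placement | SD of mean | 1.7 MVU | 5 MVU | 15 MVU |
|---|---|---|---|---|
| 63 is the SD of the mean itself | 63 | 5.2% | 6.4% | 18% |
| 63 is for one reading, equal correlation 0.7 to 0.3 | 56 to 43 | 5.2-5.3% | 6.8-8.0% | 22-33% |
| 63 is for one reading, AR(1) 0.7 to 0.3 | 52 to 39 | 5.2-5.4% | 7.1-8.7% | 25-39% |

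Example, first row: 5/(63 × 0.2236) = 0.35, giving 6.4%. A 10-minute mismatch (1.7-5 MVU) therefore gives about 5-9%.

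**4. Several time points.** In simulation with 40 per arm and no true effect, claiming success if any of four t-tests is significant gives 17/16/13% (equal correlation 0.3/0.5/0.7) and 14-18% (AR(1)). One t-test on each woman's mean holds 5%.

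**5. Precision from baseline.** The variance of the mean after ANCOVA, relative to before, is 0.811/0.600/0.368 (equal) and 0.971/0.893/0.710 (AR(1)). Estimating one covariate at N = 80 multiplies these by 77/76, so the net cut runs from 1 − 0.971 × 77/76 = 2% to 1 − 0.368 × 77/76 = 63%. Adding BMI as a second covariate (77/75) gives 0-62%.

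**The case against.** **The size of the shift is assumed.** No figure in the documents supports a drift of 10-30 MVU per hour or a systematic 30-minute mismatch. Treatment is a single oral dose with no stated delay, and staff may simply use enrolment or allocation for controls. This stands, so only the gap itself can be asserted with confidence.

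**The plan already uses baseline.** The outcome definition compares before with after. Read as a change score whose baseline moves with the clock, the shift is zero under linear drift. This also stands. A reader might infer that the plan ignores baseline, or that an unadjusted t-test would be invalid. Neither follows: baseline is in the outcome definition, and the unadjusted test is valid but may be less precise.

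**The 13-18% is conditional.** A reader might infer that it is the trial's error rate. It applies only if every time point is tested and any significant one is claimed, which the plan does not say. Tukey or Student-Newman-Keuls tests may be meant for factors with more than two levels.

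**Early endings.** A reader might expect women who deliver or lose the catheter before two hours to bias the result. If 10-20 percentage points more recordings in one arm end at 60 minutes, a mean over available readings shifts by 0.5 h × 10-30 MVU/h × 0.10-0.20 = 0.5-3 MVU. That is too small to carry the point.

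None of this supplies a control clock or names a summary of the readings.

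**Conclusion.** The point holds as a gap in specification. The stated timing rule cannot be applied to controls, and the plan names neither a summary of the follow-up readings nor the form in which baseline enters the test. Both should be settled before data are analysed.

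The consequence is a range. Under the assumed drift and a systematic 30-minute mismatch, the shift is 0-15 MVU. If a shift of 5 MVU is present the false-positive rate is about 6-9%, and for 15 MVU about 18-39%, depending on the correlation and on whether the back-solved SD of 63 belongs to one reading or to the mean. A 10-minute mismatch gives about 5-9%. The documents do not support saying that the result will be biased, or by how much.

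**What to change.** **(a) Common clock.** Suggested wording:

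> Time zero is the recorded time of allocation in both arms. Baseline is the 30 minutes before it; follow-up readings and the cervical examination are timed from it. Ingestion time is also recorded.

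State too whether readings are time points or 30-minute windows. Any delay to ingestion slightly dilutes the first interval, and 30 minutes of trace must exist before allocation; the catheter is already required before enrolment. This aligns the clocks but does not stop staff who can foresee the odd/even assignment from choosing when to enrol. The passages on the oxytocin condition must be reconciled with the common time zero, including whether baseline falls inside the study period. No view is taken on that condition.

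**(b) Named analysis.** Suggested wording:

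> Each woman's mean MVU over her available follow-up readings to 120 minutes will be compared between arms by ANCOVA with baseline MVU as covariate, reporting the adjusted difference and 95% CI. Contraction frequency and peak will be analysed in the same way, each with its own baseline.

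Tukey and Student-Newman-Keuls tests should not be used for this two-arm contrast, where they add nothing. The 5% level then holds per measure, not across the three primary measures.

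**Optional.** BMI as a covariate (as strata only if the BMI blocks are real, given the odd/even rule), a mixed model for repeated measures as sensitivity analysis, and early endings reported by arm.

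**Cost.** Low: protocol and SAP wording and a standard model. Baseline MVU is already collected. Times of allocation and ingestion are not among the listed data and must be added, as must the time and reason for the end of recording if early endings are reported.

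### Nothing masks the arm from whoever derives the primary contraction measures, although the treatment and the study number both disclose it; a masked reading step would reduce this bias

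*Combined protocol and SAP*

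**What the plan says.** All of this is in Section VI (Study Design and analysis) of the combined protocol and SAP, unless noted.

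- **Treatment.** The arms are "Control group: no medication" and "Intervention group: Calcium carbonate 500 mg 4 tablets PO x1". No placebo is described.
- **Allocation.** By number: odd goes to control, whereas "even study numbers will be in the intervention group".
- **Primary outcome.** It is "assessed by comparing Montevideo units (MVU), frequency of contractions, and peak of the contractions 30 minutes before medication administration". The follow-up readings are then taken "at 30 minutes interval for a total of 2 hours afterward".
- **Measurement.** The one safeguard is the catheter: "To ensure accuracy in MVU measurement, all patients should already have an intrauterine pressure catheter (IUPC) in place". The section does not say who derives the three measures, from what record, by what counting rule, by hand or by monitor software, or whether that person is masked.
- **Data access.** The consent part of Section V says that the data files are "accessible only to the investigators involved in the study, IRB, and IT on the ARMC server". No masked assessor is mentioned.
- **Hypothesis.** Section III states a directional hypothesis: calcium carbonate improves contractility.

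**The concern.** The catheter makes the pressure signal more accurate. It does not govern how MVU, frequency and peak are taken from that signal. If the values are read by hand, someone must decide where resting tone lies, which deflections count as contractions, and which part of a 30-minute window is usable. A person who knows the arm and expects an increase can make those choices differently in the two arms without intending to.

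Under the plan as written, that person has two routes to the arm: seeing or knowing that tablets were given, and seeing an odd or even study number. The second route matters even for someone who never met the patient.

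There is also a gap in timing. The windows are anchored to medication administration, and controls have no administration. Unless a corresponding time is fixed for them, the choice of control windows is itself open to judgement.

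What is at stake is the trial's main comparison. Without a placebo, patients and bedside staff will know the arm, but the reading step can still be masked.

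**Working it through.** **1. Can the arm be known when the outcome is derived?** The documents give a no-medication control, tablets in the other arm, numbers that map to the arm by parity, and no masking of the derivation. Nothing in the plan prevents it.

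**2. The plan's own figure.** Section V (Subject recruitment) gives a baseline of 200 MVU, a 20% difference, 80% power and 80 patients in total (40 per group). Section VI gives a significance level of 0.05. No SD is stated, and I take the test as two-sided.

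- Target difference: 0.20 × 200 = 40 MVU.
- Implied SD: 40 / [(1.960 + 0.842) × √(2/40)] = 40 / (2.802 × 0.2236) ≈ 63.9 MVU.

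So 80 cannot be reproduced from stated inputs, but it fits an SD of about 63 to 64 MVU (SD 63 gives a total of 78; SD 63.8 gives 80). I use 63, with 50 and 80 as a range.

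**3. What a differential reading shift would do (illustration).** Suppose calcium has no effect, but follow-up readings differ between arms by b MVU because of the reader. With 40 per arm, a two-sample t-test on one follow-up value per woman has standard error SE = SD × √(2/40), 78 degrees of freedom and noncentrality b/SE. The critical value is 1.991.

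For SD 63 and b = 10 (5% of 200): SE = 63 × 0.2236 = 14.09, and 10/14.09 = 0.71. The noncentral t then gives a rejection probability of 0.108.

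| Assumed SD (MVU) | SE | b = 5 (2.5% of 200) | b = 10 (5% of 200) |
|---|---|---|---|
| 50 | 11.18 | 0.073 | 0.143 |
| 63 | 14.09 | 0.064 | 0.108 |
| 80 | 17.89 | 0.059 | 0.086 |

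With b = 0 the rate is 0.05. A normal approximation gives nearly the same results (0.145 at SD 50, 0.108 at SD 63.8 and 0.086 at SD 80 for b = 10). A 10 MVU shift is a quarter of the 40 MVU target.

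**4. When the shift does not matter.** If the reader shifts baseline and follow-up in one arm by the same amount, change from baseline is (follow-up + b) − (baseline + b) = follow-up − baseline, and the shift cancels. The table therefore applies to a shift that affects follow-up readings only, or to an analysis that ignores baseline.

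**5. Work involved in masked reading.** Taking one 30-minute window before and four over the two hours after gives 5 per woman, and 80 × 5 = 400 windows from 80 recordings. N does not change.

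**The case against.** The strongest reply is that the documents do not show reading bias, only silence about reading. No reader is named and hand reading is not stated. If monitor software computes the values over fixed windows, there is little room for judgement. Nor does the plan say that tracings are filed by study number; Section V names the medical record number as the identifier in the data sets. The 5% shift has no source, the SD is back-solved, the 2.5% case is close to nominal, and a constant shift cancels in change from baseline. All of this stands. It is why the percentages are illustrations, and why a documented software derivation would answer much of the concern.

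It does not answer the main point. The plan as written leaves the derivation unmasked in an open comparison with a directional hypothesis, and the choice of segment can remain a judgement even with software.

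A reader might also infer that hiding the arm from whoever would read the tracings anyway removes the bias at almost no cost. The documents do not support that, for three reasons:

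- No such reader is identified, and an investigator who enrolled the woman or saw the tablets given may recognise a recoded tracing.
- Masking covers the reading step only.
- No staffing or cost figure is given, and 400 windows have to be prepared. If values would otherwise come from bedside or monitor charting, reading them is new work as well.

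**Conclusion.** The concern holds in a limited form. There is no placebo, the numbering discloses the arm, and Section VI provides no masking when the three primary measures are derived. Masked derivation is a better method and leaves the sample size, visits and procedures unchanged. It should be adopted. My confidence is medium, because how the values will be obtained is unstated.

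The size of the bias is unknown. The rise from 5% to about 11% rests on four assumptions: hand reading, SD near 63 MVU, a 10 MVU shift, and that shift acting on follow-up readings alone. It should not be read as this trial's false-positive rate. Masked reading would reduce reading bias; it would leave untouched both the predictability of odd/even allocation and any effect of unblinded care on contractions or on the secondary outcomes.

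**What to change.** Add to Section VI:

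1. A reference time zero for each control that matches medication administration in the intervention arm, so that the windows are fixed in the same way in both arms.
2. Export of baseline and follow-up tracings under a code unrelated to the study number, with the arm, administration marks and chart annotations removed. The code list should be held by someone other than the reader.
3. Derivation of MVU, frequency and peak by an existing study investigator who took no part in that woman's enrolment or care, under a written counting rule; or by monitor software applied identically to the fixed windows. The protocol should say which.
4. Linkage of values to arm only after all readings are locked.

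**Cost.** Existing staff recode 80 recordings (about 400 thirty-minute windows), and readings are done in batches rather than at the bedside. No patient, visit or procedure is added. The title page lists several principal investigators, so a reader outside a given woman's care may be available within the team, but the documents do not confirm this and the sponsor should check.

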- Purpose of the Study: The purpose of the study is to investigate whether calcium carbonate supplementation during labor can improve uterine contractility and decrease labor dystocia. By conducting this trial, the aim is to provide evidencebased guidance to healthcare providers regarding the potential use of calcium carbonate as a preventive measure for labor dystocia.
- Hypothesis: We hypothesized that pregnant women, those who receive calcium carbonate supplementation will have improve uterine contractility and a shorter labor course.
- Alternative Hypothesis: Calcium supplementation will have no effect on contractility

IV: Study type: Randomized control trial

V: Methods:

Location: Labor and Delivery at Arrowhead Regional Medical Center

- Start: Plan to start at the receipt of IRB approval. We anticipate the duration of the study to be about 2 years.
- Type of research: other
- Inclusion:
- Patients undergoing induction of labor with an intrauterine pressure catheter already in place at the discretion of the OB provider
- Maternal age: >18 years of age
- Gestational age > 37 weeks 0 day
- Cephalic presentation
- Able to understand/read English and/or Spanish
- Exclusion:
 - Maternal age < 18 years of age
 - Incarcerated patients
 - Active labor
 - Active illicit substance use
 - Multiple fetal gestations
 - Bleeding concerning for hemorrhage/placental abruption/placenta previa, or other contraindications to vaginal delivery
 - Aneuploidy or fetal structural anomaly
 - Prior cesarean deliveries
 - Known maternal arrhythmias, hyperparathyroidism, heart failure, kidney failure, liver failure, and history of kidney stones
 - Medications that affect uterine contractility like Magnesium, Terbutaline, Cytotec (need to be 4 hours after administration to enroll)
- Subject recruitment: All women with a term pregnancy, admitted for induction of labor will be asked to participate if age >18 years of age and English/Spanish speaking. We will plan to recruit when a patient is at least 4 cm and greater with an IUPC already in place. Using a baseline Montevideo unit of 200, if we were to aim for a 20% difference with a power of 80%, a sample size of 80 would be the minimum goal to enroll. Therefore, our goal is to enroll at least 40 patients into each group.

Consent:

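### The hypothesis of a shorter labor has no outcome that runs from allocation to delivery; the declared stage durations start elsewhere

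*Combined protocol and SAP*

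**What the plan says.** All references are to the combined protocol and SAP.

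- **Hypothesis (section III).** Women given calcium "will have improve uterine contractility and a shorter labor course".
- **Entry (section V).** The inclusion criterion is "Patients undergoing induction of labor with an intrauterine pressure catheter already in place at the discretion of the OB provider". The recruitment paragraph adds: "We will plan to recruit when a patient is at least 4 cm and greater with an IUPC already in place". Active labor is listed as an exclusion but is not defined.
- **Treatment (section VI).** After consent and allocation, one arm receives a single oral administration and the other receives no medication.
- **Primary outcome (section VI).** Contractility is tied to dosing: "30 minutes before medication administration and at 30 minutes interval for a total of 2 hours afterward".
- **Duration outcomes (section VI).** "Secondary outcomes include duration of first and second stage of labor, mode of delivery". No start point is given for the first stage, and neither duration is linked to allocation or dosing.
- **Time to delivery (section VI).** It appears in a list of other maternal information that includes "cervical dilation/effacement/station at the time of medication administration and after administration, time to delivery, oxytocin use". The stated purpose of that list is to compare the groups and rule out confounding. No time origin is given.

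**The concern.** A claim that treatment shortens labor needs a clock that starts when the arms are formed and stops when labor ends. The plan declares no such outcome. First-stage duration, on its usual meaning, began before the woman was allocated, so part of it cannot respond to treatment. Time to delivery, the collected variable closest to what is needed, is treated as a possible confounder although it can be an effect of calcium.

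At stake is the only declared time-based test of half of the stated hypothesis. With about 40 women per arm, a real shortening after dosing could be lost in the variation of the hours before it. A null result could not then be read as evidence that calcium leaves labor length unchanged.

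**Working it through.** **The plan's own figure.** The plan gives no sample size, SD or power for labor duration. Its target of 80 women (40 per arm) rests on a 20% difference from 200 Montevideo units and bears on this point only by fixing the arm size.

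**Step 1: what each possible clock measures.**

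| Clock | Starts | Consequence |
|---|---|---|
| First stage from labor onset or start of induction | Before allocation | Contains time that calcium cannot affect |
| First stage from active labor, if that follows entry | After allocation | The start may itself be shifted by treatment; time from dose to that start is dropped |
| Second stage | Full dilation, normally after dosing | Free of pre-dose time, but only part of the remaining labor |
| Time to delivery | Not stated | Usable only if its origin is allocation; not declared as an outcome |

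No declared outcome covers allocation to delivery on any reading.

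**Step 2: cost of including pre-allocation time.** Let A be first-stage time before allocation and B the time after it. Treatment shifts B only. Let r = SD(A)/SD(B) and let ρ be their correlation. Both are assumptions, since the documents give neither.

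- Var(A+B) = Var(B) × (1 + r² + 2ρr). The mean difference in hours is unchanged.
- Information kept, relative to analyzing B alone, is 1/(1 + r² + 2ρr).

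For power, take an effect on B that has 80% power at 40 per arm (two-sided 0.05, normal approximation): (1.960 + 0.842) × √(2/40) = 0.626 SD of B. Power on A+B is then Φ(2.802/√(1 + r² + 2ρr) − 1.960).

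| r | ρ = 0: information, power | ρ = 0.3: information, power | ρ = −0.5: information, power |
|---|---|---|---|
| 0.5 | 1/1.25 = 80%, 71% | 1/1.55 = 65%, 61% | 1/0.75 = 133%, 90% |
| 1 | 1/2 = 50%, 51% | 1/2.6 = 38%, 41% | 1/1 = 100%, 80% |
| 2 | 1/5 = 20%, 24% | 1/6.2 = 16%, 20% | 1/3 = 33%, 37% |

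**Step 3: where the loss vanishes.** Setting r² + 2ρr = 0 gives ρ = −r/2. Break-even is therefore at ρ = −0.25 for r = 0.5, at −0.5 for r = 1, and at −1 for r = 2.

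**The case against.** The strongest reply has four parts.

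1. *The first stage is not defined, so reading it as the whole first stage is an inference.* This stands. Because active labor is an exclusion, an active-phase definition could start after dosing. That reading does not rescue the outcome, since its clock would start at an event that treatment might bring forward.

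2. *The loss of information is not established.* This stands as to size. A negative correlation is plausible: women who labored longer before entry may have less labor left. It does not favor keeping the stage duration, however. Since 1 + r² + 2ρr = (1 − ρ²) + (r + ρ)², post-allocation time adjusted linearly for pre-allocation time has residual variance Var(B)(1 − ρ²), which is never larger than Var(A+B). Adjusting for dilation and parity captures some of that gain, not necessarily all of it.

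3. *Section VI already plans multivariate regression and compares time to delivery between the arms.* This stands in part. The plan names no covariates for a duration model, and hours labored before allocation are not among the variables listed. Comparing time to delivery as a confounding check does not make it an outcome.

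4. *This is a secondary matter.* It is. The research question in section III concerns contractility only, the primary outcome is anchored to dosing, and no power is claimed for duration.

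A reader might also infer that both stage durations contain hours beyond the reach of calcium. For a woman dosed before full dilation, the second stage lies wholly after the dose. Nor do the documents show that first-stage duration is mostly settled before treatment. No upper limit on dilation is stated, but the undefined active-labor exclusion may bar women who are nearly fully dilated.

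**Conclusion.** The point holds in a limited form. The hypothesis of a shorter labor is served only by stage durations that are not anchored to allocation, and time to delivery is placed among the confounders without an origin. That follows from the text and needs no assumption.

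The size of the harm does depend on assumptions. With independent components the information kept is 80%, 50% or 20% at r = 0.5, 1 or 2. A positive correlation makes this worse, and a sufficiently negative one removes or reverses the loss. These figures illustrate a range and are not estimates for this trial.

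A reader might infer that the comparison is biased. Under sound randomization it is not: pre-allocation time adds noise, and chance imbalance is already allowed for in the p-value. Section VI assigns arms by odd and even study numbers, which is predictable and could allow selective imbalance, but that is a separate defect. The change is worth making because it gives a better-defined outcome at almost no cost.

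**What to change.** In section VI:

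1. Define allocation as time zero in both arms, and record it for every woman.
2. Declare time from allocation to delivery, and from allocation to full dilation, as the secondary duration outcomes. State how cesarean delivery is handled in each.
3. Remove time to delivery from the list of possible confounders, and do not use it as a covariate.
4. Adjust both outcomes for parity and for cervical dilation at time zero. The plan collects dilation at medication administration, a moment that controls do not have, so dilation must be recorded at time zero in controls as well.
5. Define the start of the first stage and what the active-labor exclusion means, and reconcile that exclusion with recruitment at 4 cm or more. Report first- and second-stage durations as supporting results.

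The cost is a rewording of the outcome and analysis paragraphs, plus two recorded items: the allocation time, and dilation at that time in controls. Results will be slightly less comparable with papers that report total stage length, which the supporting results partly offset.
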